Study Aims:	
Aim 1: To show efficacy of 12-weeks of sodium nitrite treatment to improve mitochondrial energetics.
 
Aim 2: To show efficacy of 12-weeks of sodium nitrite treatment to improve skeletal muscle perfusion.
 
Aim 3: To explore the effects of nitrite-induced changes in mitochondrial energetics on CRF and metrics of clinical function.
 
Overall, this protocol lays a mechanistically-oriented foundation for future studies to definitively assess the utility of nitrite treatment as an important therapeutic option for the growing burden of sedentariness in old age

Study Design:	Prospective, randomized, placebo-controlled, double-blinded trial at 2 clinical sites to study the utility of a 12-week intervention (oral nitrite capsules vs. placebo) in older (age $\geq 70$ years) healthy, sedentary adults (<1 hour of structured PA per week).
Planned Sample Size:	70 participants total
Duration of Treatment:	14 weeks (12 weeks of Intervention with 2 weeks of Post-intervention testing)
Major Inclusion Criteria:	
 
• Age <math>\geq 70</math> years
 
• Sedentary (<1 hour/week of volitional exercise activity)
 
• Clinically stable (euvolemic; baseline HR <math><100</math> bpm) and without hospitalization or invasive cardiac procedure for 6 weeks
 

Major Exclusion Criteria:	See complete list in section 3.3

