### **Pre-drug baseline study visits (Visits 1- 4)**

#### **Visit 1**

Participants will be encouraged to have a light meal prior to arrival.

1. Interval history, vital signs, and a brief physical exam.
2. Exercise testing:
  - a. **Cardiopulmonary Exercise Testing (CPET)**: A symptom-limited (maximal) graded cycle ergometer exercise test in association with air-gas-exchange, an optimal gauge of aerobic capacity will be conducted by trained research exercise physiologists. A study clinician will be immediately available if needed. A computerized cycle ergometer will be used to generate a symptom-limited exercise stimulus. ACSM criteria for starting and stopping will also be utilized. A face mask or mouthpiece will be positioned over the subject's mouth and nose during the exercise for gas exchange assessments. VO2, minute ventilation (VE)/exhaled carbon dioxide (VCO2) slope, and respiratory exchange ratio (RER) will be measured as well as hemodynamics (max HR and BP), time, and ECG waveforms). Any unexpected abnormalities will be reported to the participant's primary provider(s); continued participation in the study will require the primary provider's clearance. The rate of perceived exertion (RPE) will be completed during the CPET.
  - b. **400-meter corridor walk**: Participants will walk over a 400-meter course. During the 400-meter corridor walk, average VO2 per lap during steady-state

(2 minutes of plateaued  $\text{VO}_2$ ) will be used to calculate the energy cost of walking by normalizing the  $\text{VO}_2$  to lap gait speed (ml/kg/m).

- c. For participants with diabetes, they will be asked to bring their own glucometer to assess glucose before and after the CPET.
- d. **NIRS**: NIRS will be worn during the CPET and 400-meter corridor walk. Sensors will be placed on the skin of one leg to allow the non-ionizing, LED light source to assess tissue oxygenation and perfusion via measurements of the optical absorption of hemoglobin.
- e. **Accelerometry**: An ActiGraph wrist accelerometer will be worn during the 400-meter corridor walk to establish baseline activity parameters and during the CPET.

3. A battery of questionnaires will be administered.
  - a. The following questionnaires will be administered:
  - b. Community Healthy Activities Program for Seniors (CHAMPS)
  - c. Fried Frailty Index
  - d. EuroQol

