  - e. Montreal Cognitive Assessment
  - f. Patient Health Questionnaire (PHQ-2)
  - g. PROMIS-Sleep Disturbance Short Form  
(<https://www.ncbi.nlm.nih.gov/pmc/articles/PMC3261577/>)
  - h. Self-efficacy: Sullivan
4. Participants who fail to meet applicable inclusion/exclusion criteria based upon the results of the screening assessment will be excluded from further study participation. Such participants will be paid for the visit.
5. Prior to departing, participants will be reminded to resume their usual medication regimen and clarify any modifications related to the study if indicated.

## Visit 2

Participants will be encouraged to eat a light breakfast prior to arrival.

1. Interval history, vital signs, and a brief physical exam.
2. Steady-State Walking Test: A steady-state walking (1.5 mph) test will be completed on a treadmill. Participants will wear a portable CPET device during the steady-state walk. The rate of perceived exertion (RPE) will be completed during the steady-state walking test.
3. Submaximal CPET: the participant will pedal on a cycle ergometer with a fixed resistance (the resistance associated with 60%-80% peak  $\text{VO}_2$  achieved during the initial symptom-limited CPET on visit one). The rate of perceived exertion (RPE) will be completed during the submaximal CPET.
4. Handgrip Strength Assessment
5. Short Physical Performance Battery (SPPB) will be completed:
  - a. Sitting and standing out of a chair

- b. Walking over a 4-meter course (to measure walking speed)
  - c. Standing with their feet in different positions to measure their balance
6. NIRS will be worn during the submaximal CPET. NIRS and ActiGraph will be worn during the steady-state walk.
7. Standard breath-by-breath CPET ventilatory indices  $VO_2$ ,  $VE/VCO_2$ , and RER will be collected and used to characterize the performance during the submaximal CPET as well as the steady-state treadmill walk completed in this study visit.
8. Three-day food record (3DFR): participants will be provided forms to complete a 3DFR which will be analyzed for plant-based dietary nitrite and nitrate. Participants will be assigned dates for these self-assessments, including one weekend day. Participants will be asked to maintain a diet that is consistent throughout the trial. Major dietary modifications during the 16-week trial will be discouraged.

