### **2.3.10 Randomization and Blinding:**

We will use the high quality pseudo-random deviate generator in SAS® (SAS Institute, Inc., Cary, North Carolina) to randomize participants to NO or placebo in 1:1 ratio. Because of the moderately large sample size and the resulting opportunity for participant characteristic imbalance between the arms and the threat it would pose to internal validity, we will employ an adaptive randomization scheme to ensure balance by design rather than chance with respect to some key characteristics. Specifically, stratified by study site, we will use a variation of the minimization algorithm that can account for both continuous and categorical variables to ensure balance with respect to gender and walking speed with 80% biased coin probability; and simultaneously guard against heavy sample size imbalance. Such adaptive schemes have been shown to be valid alternatives in trials. Study personnel will call in all prescriptions to the independent research pharmacist at the institutional Investigational Drug Service (See Resources and Environment), who will package all drugs/placebos to be similar in physical appearance. We have successfully employed the same process in other recently completed trials. Therefore, all participants and study personnel (except the study statistician and the dedicated provider of clinical care related to study safety) involved in assessments will be blind to treatment assignment.

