## **2.4 STATISTICAL ANALYSIS**

### **2.4.1 Sample Size Justification**

The principle focus of the proof of mechanism trial is the impact of nitrite on mitochondrial energetics. To detect a significant difference in mitochondrial state 3 respiration in permeabilized fibers (the primary outcome for Aim 1), the planned sample size is 35 per group (a total of 70 participants). Respiration data from a previous multi-site RTC that was co-led by [name], showed a baseline values of  $270.30 \pm 99.80$  pmol/min/mg (mean  $\pm$  standard deviation) for State 3 respiration and a pre- to post-intervention change of  $68.5 \pm 97.61$  pmol/min/mg We conservatively anticipate a dropout rate of approximately 14%. Using published methods implemented in commercial software (PASS 2012®, Number Cruncher Statistical Systems, Kaysville, Utah), with 70 patients and 60 anticipated completers, we will be able to detect statistical significance of a difference as small as 71.80 pmol/min/mg in pre- to post-nitrite change with 80% power in a 2-tailed test at the  $\alpha=0.05$  level. The criterion for a minimally clinically important difference (MCID) has not been authoritatively established for the measure, but the above detectable difference corresponds to a moderate to large effect size ( $d=0.74$ ) by Cohen's criterion. Therefore, the planned sample size affords an appropriate level of statistical sensitivity to address the aims in a mechanistic study with proximal biological outcomes such as ours.

For Aim 3, with the anticipated 30+30 completers, we will be able to detect statistical significance of correlations as small as 0.49 and 0.35, respectively, between changes in mitochondrial energetics and changes in physical activity/function and fatigability with 80% power in two-tailed tests at  $\alpha=0.05$  conducted without and with stratification by treatment group. As such, the planned sample size will afford sufficient statistical sensitivity to detect even moderate associations between mitochondria respiration and clinical endpoints.

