### **2.4.2 Data Analysis**

Overview: All statistical analyses will be performed and overseen by the study statistician [name] (see LOS) using SAS® version 9 (SAS Institute, Inc., Cary, North Carolina). Participant

flow will be summarized using a CONSORT diagram. Data will be summarized by intervention arm and time point as well as baseline to follow-up change using appropriate descriptive statistics. First, the baseline participant characteristics will be compared between the two arms. Any significant differences will be noted and accounted for as additional covariates in the sensitivity analyses. Second, main analyses to address the aims will be performed as outlined below using multiple imputation for missing data. The primary analysis will be performed to test the primary hypotheses H1a about the primary outcome of mitochondrial respiration (high resolution respirometry). Secondary analyses will be performed for remaining hypotheses, secondary outcomes and other exploratory analyses. Third, we describe below our primary approach to missing data and a set of sensitivity analyses by including additional covariates and ignoring missing data.

**Baseline Comparison:** Due to the adaptive randomization scheme, it is unlikely that baseline participant characteristics will be significantly different between the arms. If we do find any, they will be included as additional covariates in the sensitivity analyses. We will not alter the primary analytic strategy to preserve its a priori nature and predictability. We will use independent samples t- or Wilcoxon rank sum tests, as appropriate based on distributional properties, to compare continuous baseline characteristics between the intervention arms. For categorical baseline participant characteristics, we will use chi-square and Fisher's exact tests, as appropriate. Statistical significance of the intervention term will be interpreted as indicating the need to include them as covariates in sensitivity analyses.

**Aim 1 Analysis:** Analysis of covariance (ANCOVA) model using the SAS® GLM procedure with baseline to follow-up change in mitochondrial respiration (high resolution respirometry) as the dependent variable, intervention arm (nitrite/placebo) as the effect of main interest, and the baseline value of mitochondrial bioenergetics as a covariate. The magnitude and statistical significance at  $\alpha=0.05$  of the nitrite vs placebo contrast will serve as the formal test of the primary hypothesis H1a.

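### The primary, secondary and H3a models leave out the factors used to allocate patients (site, gender, walking speed), so the tests are conservative and lose some power if those factors predict the outcome

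*Combined protocol and SAP*

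**What the plan says.** - **Allocation (2.3.10).** Randomisation is 1:1 and adaptive: "stratified by study site, we will use a variation of the minimization algorithm", used "to ensure balance with respect to gender and walking speed with 80% biased coin probability". The Synopsis describes a "double-blinded trial at 2 clinical sites".
- **Primary analysis (2.4.2, Aim 1).** This is an ANCOVA of change in respiration with "intervention arm (nitrite/placebo) as the effect of main interest, and the baseline value of mitochondrial bioenergetics as a covariate". No other term is listed.
- **Other models (2.4.2).** Secondary outcomes measured only before and after treatment follow the same ANCOVA. The H3a mixed models contain arm, time, their interaction, the outcome's own baseline and a participant random effect.
- **Additional covariates (2.4.2, Baseline Comparison and Sensitivity Analyses).** Gender enters one sensitivity analysis. Any other characteristic joins it only if it differs significantly between arms at baseline. The plan considers such differences unlikely because of the adaptive scheme, and it keeps the primary model fixed so that it stays pre-specified.
- **Power (2.4.1).** The calculation is "with 70 patients and 60 anticipated completers", giving "a difference as small as 71.80 pmol/min/mg in pre- to post-nitrite change with 80% power", two-sided at 0.05.
- **Walking speed.** Section 2.2.1 measures it twice at baseline: as lap gait speed in the 400-metre corridor walk (Visit 1) and over 4 metres in the SPPB (Visit 2). Section 2.3.10 does not say which one is minimised.

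**The concern.** When allocation balances a factor that predicts the outcome, the arm difference varies less from one hypothetical trial to the next than under simple randomisation. A model without that factor does not register this. It leaves the factor's variance in the residual, so the standard error is too large, the test rejects too rarely under the null, and power is given up.

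The route by which site or walking speed could still enter is nearly closed. It requires a significant baseline difference in exactly the factors that the scheme balances, and it leads only to a sensitivity analysis. The wish for a fixed primary model is sound, but covariates named in advance meet it equally well.

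**Working it through.** **1. The plan's own figure.** Two-sample t-test, 30 completers per arm, SD of change 97.61 (2.4.1): d = 71.80/97.61 = 0.7356. With 58 df, power is 79.996%, so the stated 80% is reproduced.

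**2. Residual SD once baseline is in the model.** Section 2.4.1 gives a baseline SD of 99.80 and a change SD of 97.61. The post-treatment SD is not given.

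- If it equals the baseline SD: ρ = 1 − 97.61²/(2 × 99.80²) = 0.522. Residual SD = 99.80 × √(1 − 0.522²) = 85.1, and d = 71.80/85.14 = 0.843.
- The residual SD cannot exceed the change SD. It reaches 97.61 when baseline and change are uncorrelated, which needs a post SD of √(99.80² + 97.61²) = 139.6. Then d = 0.736.
- For post SDs of 80, 90, 99.8, 110, 120 and 139.6, the residual SD is 72.3, 79.2, 85.1, 90.3, 94.2 and 97.6. Planned power is 96.6, 93.2, 89.4, 85.7, 82.7 and 80.0%.

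**3. The mechanism in closed form.** Suppose the three factors explain a share R² of the variance left after baseline, and balance were perfect. The true standard error would be √(1 − R²) times the one the planned model reports. In the normal approximation the nominal 5% test would then have size 2 × [1 − Φ(1.96/√(1 − R²))]: 3.9% at R² = 0.10, 2.8% at 0.20 and 1.9% at 0.30. Real balance is imperfect, so the actual shortfall should be smaller.

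**4. Simulation.** Seventy patients were minimised within site on arm size, gender and walking speed with an 80% biased coin, and 60 completed at random. The ANCOVA was fitted with and without the three factors. Base case: equal sites, 20,000 trials. R², the exact algorithm, its weights, the site split and equal contributions of the factors are assumptions.

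| Assumed R² after baseline | 0 | 0.10 | 0.20 | 0.30 |
|---|---|---|---|---|
| Type I error, planned (%) | 4.8 | 4.1 | 3.4 | 2.6 |
| Power at 71.80, planned (%), residual SD 85.1 | 89.0 | 89.8 | 90.6 | 91.5 |
| Power at 71.80, adjusted (%), residual SD 85.1 | 88.6 | 91.5 | 94.4 | 96.6 |
| Change in points, residual SD 85.1 | -0.4 | +1.7 | +3.7 | +5.1 |
| Change in points, residual SD 97.61 | -0.5 | +2.5 | +5.6 | +8.7 |

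The adjusted model holds about 5% type I error. Monte Carlo error is about 0.15 to 0.25 points for type I error and 0.2 to 0.5 for power.

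**5. Robustness.**

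- *Allocation.* Variants with less weight on speed, dichotomised speed, an 80/20 site split or a single site (10,000 trials each), together with the base case, give changes of -0.1 to -0.9, +1.5 to +1.9, +3.5 to +4.0 and +4.9 to +5.6 points at residual SD 85.1.
- *Multiple imputation with M = 5, as planned* (8,000 trials). Changes are -1.1, +1.9, +3.7 and +6.2 points at residual SD 85.1, and -1.1, +2.6, +6.2 and +10.4 at 97.61.
- *Cause.* In a separately coded simulation (6,000 trials, residual SD 97.61), the planned model's mean standard error was 25.4 against a true 23.7 at R² = 0.20, and 25.4 against 22.4 at 0.30. With arm labels permuted at random, its type I error was 5.0 to 5.6%. The conservatism therefore comes from the balancing.
- *Significance selection.* A baseline test at 0.05 picked walking speed in under 1% of trials in every variant. This is indicative only.
- *H3a mixed model.* A generic version (two follow-ups, random intercept, assumed intraclass correlation 0.4 to 0.8, 8,000 trials) had planned type I error of 4.2–4.3, 3.4–3.6 and 2.7–2.9% at R² of 0.10, 0.20 and 0.30. The gains at d = 0.843 were +1.7 to +2.0, +3.4 to +3.6 and +4.9 to +5.2 points.

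**The case against.** The strongest reply is that nothing the plan promises fails. The test is valid and pre-specified, and it meets its power target. The loss is only a forgone gain, and its size rests on an R² that the documents do not support. Baseline respiration may already absorb much of any link between walking speed and mitochondrial function. R² of 0.20 or 0.30 means a multiple correlation of √0.20 = 0.45 or √0.30 = 0.55 with the residual change, which is demanding for three baseline factors. For scale, Section 2.4.1 calls correlations of 0.35 to 0.49 between concurrent changes moderate. The minimisation algorithm is also only outlined, so the simulated scheme is a reconstruction.

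This stands as a limit on size. At R² up to 0.10 the effect is small, and the larger gains need both a high R² and, above about 6 points, the extreme residual SD. It does not remove the point, because the direction held in every allocation variant and the change costs almost nothing.

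Two objections concern the remedy. For an H3a outcome whose own baseline is the minimised speed, the walking-speed term would duplicate a term already present. If only one site enrolled, a site term could not be estimated; the procedures section names only Pittsburgh facilities, although the Synopsis and Section 1.2 state two sites. In either case the term is aliased and drops out without changing the arm contrast. For other walking outcomes the gain may simply be smaller.

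**Conclusion.** The concern holds. No main model contains a factor used for allocation, and only gender is assured of a place in even a sensitivity analysis. If the factors predict the outcome after baseline, the H1a test is conservative and some power is given up. This is purely a matter of efficiency and of a correct standard error. If the factors predict nothing, omitting them costs nothing.

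The omission and the direction are firm. The size is conditional: small at R² up to 0.10, moderate above that, and less if the post-treatment SD is below the baseline SD. Confidence is medium for that reason. The change should be made because the stakes are asymmetric: about 1 point of power or less at risk, against roughly 4 to 6 points at R² = 0.20. The unnamed walking-speed measure needs settling whatever R² turns out to be.

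**What to change.** - **Primary ANCOVA:** change = arm + baseline respiration + site + gender + walking speed. Use the same continuous walking-speed value that enters the minimisation.
- **Secondary ANCOVAs and H3a mixed models:** add the same three covariates. State that a term is dropped where it duplicates the outcome's own baseline, or where only one site enrols.
- **Section 2.3.10:** state which walking speed is minimised, the 4-metre SPPB speed or the 400-metre lap speed.
- **Sensitivity analyses:** keep the arm-plus-baseline model here, and remove the selection of covariates by baseline significance tests.

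The cost is SAP wording only, since all three values are already needed for randomisation. With 60 completers the residual degrees of freedom fall from 60 − 3 = 57 to 60 − 6 = 54. If the factors carry no information, that costs 0.1 to 1.1 points of power over all runs.

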#### 1.2 SPECIFIC AIMS

Two-site randomized controlled trial to clarify the impact of a 12-week course of nitrite supplements versus placebo on mitochondrial energetics in older sedentary adults. We will take an integrative physiology approach to determine the effect of nitrite therapy on a comprehensive assessment of mitochondrial energetics, skeletal muscle vascular function, and whole-body physical function (cardiorespiratory fitness [CRF], exercise endurance, strength, balance, and daily physical activity [PA]) and fatigability.

**Aim 1:** To show efficacy of 12 weeks of sodium nitrite treatment to improve mitochondrial energetics.

- We hypothesize that compared to placebo, the participants receiving nitrite supplements will show an improvement in:

H1a: Skeletal muscle mitochondrial respiration, efficiency (high resolution respirometry [primary outcome]) and adenosine triphosphate (ATP) production (phosphorus-magnetic resonance spectroscopy)

H1b. Morphology and molecular underpinnings of muscle energetics (Direct Immunofluorescence and light microscopy of mitochondrial structure, RNA-Seq and Western Blot)

**H1c: Platelet mitochondrial respiration (Seahorse), i.e., an analysis to clarify whether platelets can be used as a surrogate to skeletal muscle to assess equivalent changes in mitochondrial bioenergetics**

**Aim 2:** To show efficacy of 12 weeks of sodium nitrite supplements to improve skeletal muscle perfusion.

- We hypothesize that, compared to placebo, the nitrite group will show a greater improvement in:

**H2a:** Tissue oxygenation, as measured using near infrared spectroscopy (NIRS) during exercise.

**Aim 3:** To explore the effects of nitrite-induced changes in mitochondrial energetics on CRF and metrics of clinical function.

- We hypothesize that, compared to placebo, the participants receiving nitrite supplements will show a greater improvement in:

**H3a:** Increased CRF (peak oxygen uptake [ $\text{VO}_2$ ] achieved during progressive resistance on a cycle ergometer), increased endurance (duration of exercise at fixed resistance 60%-80% peak  $\text{VO}_2$  intensity), increased efficiency of walking (decreased  $\text{VO}_2$  at steady-state [1.5 mph] and self-paced walking), increased 400-meter corridor walk, increased SPPB score; increased handgrip strength, increased PA (accelerometry), and decreased fatigability (during steady-state walking and 400-meter corridor walk respectively).

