**H3b:** Changes in mitochondrial energetics and skeletal muscle perfusion induced by nitrite will be associated with changes in daily activity (measured by accelerometry), and fatigability (measured by rate of perceived exertion during steady-state [1.5 mph] walking).

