- The skeletal muscle mitochondrial assessments will be coupled with an analysis of platelet mitochondrial energetics (Seahorse) to determine the utility of platelet measurements to be applied as (1) a novel and convenient biomarker of mitochondrial energetics.
- NIRS will be used to assess: (1) skeletal muscle mitochondrial metabolic performance profile during the hypoxic stress by gauging perfusion changes pre- and 12-week post-nitrite versus placebo. Clinical and Physiological assessments:

Fitness and Efficiency (1) CRF (peak VO2) on a progressive intensity cycle ergometer will clarify how changes in mitochondrial respirometry translate into systemic oxygen utilization, highlighting physiological linkage between cellular respiration and whole-body oxygen utilization and putative benefits of nitrite to improve these relationships; (2) VO2 at 60%-80% exercise resistance (watts) on a cycle ergometer until exhaustion will assess nitrite-mediated changes in endurance; (3) VO2

at a steady-state walking (1.5 mph) will assess nitrite-mediated changes in the efficiency of walking and associated perceived fatigability (changes in rated of perceived exertion); (4) 400-meter corridor walk (with portable gas exchange) will be used to assess overall capacity (disability), physical fatigability (slowing of walking speed), as well as the energy of walking.

Additional functional measures: (1) short physical performance battery (SPPB) to assess strength, balance, and an index of frail; (2) handgrip to assess strength; (3) daily activity (accelerometry).

Fatigability: Fatigability assessments are novel, and include both “perceived” (rate of perceived exertion [RPE]) during steady-state walking, as well as “performance” (energy consumed during a 400-meter corridor walk) subtypes.

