We will employ the same analytic strategy described above for the primary outcome mitochondrial respiration for each of our remaining secondary continuous outcomes of mitochondrial bioenergetics, skeletal muscle perfusion and clinical measures collected only pre- and post-intervention. The magnitude and statistical significance of the nitrite vs placebo contrasts will serve as formal tests of the hypotheses H1b-c and H2a-b.

**Aim 2:** For physical function and activity measures additionally assessed midway, and hypothesis H3a, we will instead employ a linear mixed model to accommodate multiple post-randomization assessments and the resulting stochastic non-independence of observations. Specifically, we will fit a series of linear mixed models with change from baseline in each measure of physical function/activity as the dependent variable; intervention arm (nitrite/placebo), follow-up time (mid-course assessments and 12 weeks) and their interaction as fixed effects; baseline value of the dependent variable as a fixed-effect covariate; and a participant random effect to account for multiple observations from each participant. We will appropriately construct means contrasts to make comparisons between intervention arms at each of the follow-up time-points, and interpret their statistical significance as supporting hypothesis H3a.

**Aim 3 (hypothesis H3b) Analysis:** We will examine whether changes in mitochondrial energetics, muscle perfusion and physical function/activity/fatigability tend to move at least partially in unison. We will compute Pearson and Spearman rank correlations between pre- to post-treatment changes in the above measures over the treatment period. We will consider correlations both with and without stratification by treatment group. We will also consider adjusting for baseline values of the measures considered and obtain partial correlation coefficients to isolate the associations in changes above and beyond any cross-sectional associations at baseline and comparing the correlations between groups using the Fisher's z-transformation. Finally, we will explore multivariable linear regression models with change in measures of physical function/ac-

tivity as the dependent variable; treatment group, and baseline and changes in measures of mitochondrial energetics as independent variables, taking care not to exceed the number of independent variables that could be realistically afforded by the effective sample size.

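### The arm contrast named as the formal test of H1c cannot show whether a participant's platelet change tracks that participant's muscle change, and no planned analysis names that pair

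*Combined protocol and SAP*

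**What the plan says.** Section 1.2 places H1c under a stem that predicts improvement against placebo, and then describes it as "an analysis to clarify whether platelets can be used as a surrogate to skeletal muscle to assess equivalent changes in mitochondrial bioenergetics". Section 1.4 gives the same reason for coupling the platelet assay to the muscle work: "to determine the utility of platelet measurements to be applied as (1) a novel and convenient biomarker of mitochondrial energetics".

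Section 2.4.2 applies the Aim 1 ANCOVA (change as outcome, with arm and a baseline value as predictors) to each secondary outcome in turn, and states: "The magnitude and statistical significance of the nitrite vs placebo contrasts will serve as formal tests of the hypotheses H1b-c and H2a-b".

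The only correlation work sits under Aim 3, hypothesis H3b: "We will examine whether changes in mitochondrial energetics, muscle perfusion and physical function/activity/fatigability tend to move at least partially in unison". It allows for partial correlations: "We will also consider adjusting for baseline values of the measures considered and obtain partial correlation coefficients". In section 1.2, H3b concerns energetics and perfusion changes that "will be associated with changes in daily activity (measured by accelerometry), and fatigability". The correlation power statement in section 2.4.1 covers associations "between changes in mitochondrial energetics and changes in physical activity/function and fatigability with 80% power".

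Section 2.2.1 has platelet respirometry drawn before the dose and at 30 minutes at Visits 4 and 5. Visit 9 follows the Visit 4 blood schedule. At Visits 4 and 9 one biopsy precedes the dose and a second follows the 30-minute blood draw.

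**The concern.** A surrogate claim about change needs evidence that the two tissues change together within people. The test named for H1c uses platelet data alone. An arm effect in platelets is compatible with no within-person relation to muscle, and a close relation is compatible with no arm effect.

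If the plan is followed literally, the formal test of H1c may be significant and H1c may be written up as supported, although nobody has looked at whether platelets follow muscle. The time-matched blood and biopsies needed for that analysis will have been collected from participants anyway.

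**Working it through.** **1. The plan's own figures reproduce.** Inputs from section 2.4.1: SD of change 97.61, detectable difference 71.80, 30 completers per arm, two-sided 0.05.
- Two-sample noncentral t: power at 71.80 is 0.80, with d = 71.80/97.61 = 0.74.
- Detectable correlation = tanh[(1.960 + 0.842)/√(N − 3)]. N = 30 gives tanh(2.802/5.196) = 0.49; N = 60 gives tanh(2.802/7.550) = 0.35. These are the two values listed. The section attaches 0.49 to the unstratified test and 0.35 to the stratified one, the reverse of what these sample sizes imply. That does not affect this point.

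The documents give no figure for H1c.

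**2. What the named test responds to.** The ANCOVA for platelets has no muscle variable, so its result cannot depend on the within-arm platelet-muscle correlation. A simulation illustrates this. Assumptions: 30 per arm; equal effects in both tissues; pre-post correlation borrowed from the muscle SDs, 1 − 97.61²/(2 × 99.80²) = 0.52, taking pre and post SDs as equal; 8,000 trials per cell. No platelet effect or SD is documented, so a range is shown. Percentage of trials in which the platelet contrast is significant:

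| Platelet effect (SD of change) | Within-arm r = 0 | Within-arm r = 0.36 |
|---|---|---|
| 0 | 4.7 | 5.0 |
| 0.3 | 25.2 | 25.7 |
| 0.5 | 58.1 | 58.4 |
| 0.74 | 89.3 | 89.9 |

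The analytic powers (effect d/√[(1 + 0.522)/2], 57 df) for the last three rows are 25.8%, 58.8% and 89.8%. Down each column, the contrast responds strongly to the size of the platelet effect. Across each row, it does not respond to tracking.

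**3. Precision of the missing analysis.** For a partial correlation with k covariates, replace N − 3 by N − k − 3.
- Arm only (k = 1), N = 60: tanh(2.802/√56) = 0.36. With 50 analysed it is tanh(2.802/√46) = 0.39; with 70, tanh(2.802/√66) = 0.33.
- Arm and both baselines (k = 3), N = 60: tanh(2.802/√54) = 0.36. With 50 it is 0.40; with 70, 0.34.
- 95% CI at r = 0.36, N = 60: tanh(0.377 ± 1.96/√56) = 0.11 to 0.56 for k = 1, and tanh(0.377 ± 1.96/√54) = 0.11 to 0.57 for k = 3.

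**4. Which adjustment should lead.**
- No adjustment: if both tissues shift by 0.736 SD and are unrelated within arms, the pooled correlation is (0.736²/4)/(1 + 0.736²/4) = 0.12. This comes from the arm difference alone, so arm must be adjusted for.
- Baseline adjustment: if usual platelet and muscle levels correlate 0.3, 0.5 or 0.7 but changes are unrelated, the baseline-adjusted value averages 0.05, 0.09 and 0.14, and is significant in 6.5%, 10.8% and 18.3% of 5,000 simulated trials. The arm-only value averages 0 and is significant in about 5%. The arm-only version should therefore lead.

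**The case against.** The best defence has three parts.

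First, the named test fits the stem of H1c. The surrogate wording follows as an explanatory gloss, not as a separate lettered hypothesis. This stands: the contrast is the right test of improvement and should be kept.

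Second, the contrast does bear on surrogacy. A reader might infer from the table that it says nothing about the surrogate question. The documents do not support that. The same ANCOVA is run on muscle for H1a, so the two contrasts can be read together. If muscle responds and platelets do not, that counts against platelets as a marker, and the contrast separates no platelet effect (about 5% significant) from a 0.74 SD effect (about 90%). The partial correlation has the opposite blind spot: with arm removed, it cannot show whether platelets respond to nitrite at all. Each covers what the other misses.

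Third, platelets could fall under mitochondrial energetics in the H3b correlations, since Aim 1 carries that name and contains H1c, and the overview of section 2.4.2 leaves room for exploratory work. This is a possible reading, and the method is indeed already in the plan. But the paragraph is tied to H3b, the power statement concerns activity, function and fatigability, and no platelet-muscle pair is named.

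A reader might also infer error inflation from having both a pre-dose and a 30-minute platelet sample. No text says that either may be reported as the H1c test, so that does not follow. The Visit 4 pre-dose draw is labelled as baseline. The phrase "clinical measures collected only pre- and post-intervention" sits awkwardly with the Visit 5 platelet draw, but it may qualify only the clinical measures, and ANCOVA at Visit 9 is the natural reading. Naming the Visit 9 sample is a clarification only.

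**Conclusion.** The point holds in a limited form. The formal test of H1c covers improvement and group-level response. It leaves unexamined the within-person tracking that the surrogate clause and the biomarker aim need, and no analysis is named to fill that gap. This follows from the model's structure and does not rest on the assumed platelet effect or on the borrowed pre-post correlation. Those assumptions set only the simulated percentages. The precision figures assume 60 participants with paired platelet and muscle changes.

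Severity is low. H1c is secondary, platelets are not among the synopsis endpoints, and the primary test of State 3 respiration is unaffected.

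**What to change.** 1. State that the ANCOVA arm contrast tests the improvement part of H1c only and is not by itself evidence of surrogacy.
2. For the surrogate part, name the arm-adjusted partial correlation, with 95% CI, between change in platelet respiration and change in muscle State 3 respiration from Visit 4 to Visit 9. Use the biopsy that supplies the primary outcome and its time-matched blood: pre-dose blood with the first biopsy, 30-minute blood with the second. The documents do not say which biopsy supplies the primary value, so name it once for both analyses. The Visit 4 30-minute sample already follows a first dose, so it is not a drug-free baseline.
3. Report the version adjusted also for both baseline values as supportive.
4. Present the correlation beside the platelet and muscle arm contrasts, and state that correlated change is necessary but not sufficient for surrogacy.
5. As a clarification, name the Visit 9 platelet sample used in the arm contrast.

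The cost is some SAP wording and a few lines of code, with no new samples or visits. The drawback is one more secondary analysis of limited precision: a true correlation below about 0.36 may well be missed, and even at 0.36 the interval runs from about 0.11 to 0.56.
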